## Hypothesis

We anticipate better outcomes in literacy and decision-making capacity with more interactive intervention i.e. video educational session as compared to education delivered via a brochure.

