## Scientific Endpoints

### Response:

As a result of participation in the interactive educational sessions, we aim to demonstrate

1. Improved health literacy in Opioid Agonist Treatment (OAT) patients
2. Improved decision making among OAT patients

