## Study Design

We will start with a retrospective chart review to extract information about patient demographics, which will include age, gender, race/ethnicity, educational status, marital status, and history of mental health problems, information about substance abuse & status of hepatitis C, occupational and employment status. Some of this information will be required to decide matching factors between the clinics.

We will employ an observational two-group method design to evaluate the effect of video or computer-based education as a determinant of seeking treatment for HCV among patients on opioid agonist therapy (OAT). Group A will receive the video class intervention on the computer administered by an on-site facilitator, while “group-B” will receive an HCV educational brochure. The two groups are matched in 1:1 fashion to make the two groups similar with respect to the certain key characteristics, such as race, sex, age etc. The outcome variable is the percentage of the individuals in the two groups that retain HCV-knowledge. We expect up to 2-3 clinics to participate.

These intervention will occur after pre-test assessment by a designed questionnaire, which will include questions from different aspects of hepatitis-C infection disease process. Patients will not be notified of their questionnaire score. We will assess the questionnaires reliability and accuracy among a patient sample drawn from the clinics where the questionnaires will be deployed. We will also convey a committee of experts who will provide input on the design of the educational intervention. The last step before analysis will be post interventional assessment with the same questionnaire used for pre-intervention assessment. At the end of the study, we plan to utilize the data for analysis and manuscript preparation.

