## **Procedures Involved**

We plan to conduct a study involving 2 groups. One group consists of the intervention subjects and other of the control subjects. The intervention subjects will receive the computer-based video education, while the “control group” will receive the brochure-based intervention. The goal is to evaluate the effect of education on health literacy in people with hepatitis C and currently on opiate replacement therapy. We also plan to evaluate the willingness for treatment in people with active hepatitis C infection.

We will start with a feasibility survey to assess the patient demographics at all clinic sites where this study will be conducted. We will also conduct cognitive testing of the survey instruments to be administered to ensure reliability and accuracy. We will also request that patient partners and subject matter experts provide guidance on the educational intervention to be delivered. The study flyers for advertisement will be distributed at all the clinic sites. Patients will be given information about the study. In case of agreement to participate, informed consent will be obtained. After enrollment of the population of interest, we will start the retrospective chart review in order to extract information about patient demographics, which will include age, gender, race/ethnicity, educational status, marital status, and a history of mental health problems, information about substance abuse & status of hepatitis C, occupational and employment status.

After that information is collected, we plan to designate the population in 2 groups i.e. Intervention & Control. The next step will be the educational intervention in group A which will consist of distribution of HCV educational brochure. Similarly group B will have the video class intervention on the computer administered by an on-site facilitator. These interventions will occur after the pre-test assessment by a designed questionnaire which will include questions on different aspects of hepatitis-C infection disease processes. Finally, we will administer a post interventional assessment with the same questionnaire used for pre-intervention assessment. For patients with history of HCV infection irrespective of treatment, an additional section will be added to check their willingness for treatment.

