To understand the impact of clinic and individual patient characteristics on the HCV seropositive individuals, we will begin with building logistic regression models. If the outcome variable is defined as "1" when an HCV seropositive individual is identified and "0" otherwise, logistic regression will provide the association of HCV seropositivity as a function of clinic and individual characteristics. Further, to understand the changes in these percentages over time, we will perform a trend analysis at the minimum.

We will test the differences between the scores obtained on the post-intervention assessment and the 1-month follow up assessment. We will assess the distribution of the scores. Modeling will be done using generalized linear mixed-effects models or an alternative appropriate approach. We will include demographic factors and other covariates as appropriate.

Power/Sample Size:

The following table shows the sample size needed per group, as a function of the difference in the proportion of patients from both clinics who appear for the first appointment and the desired power of the test. The level of significance is 0.05.

| Differences in proportions | Power | |
|----------------------------|-------|------|
| | 0.80 | 0.90 |
| 0.10 | 293 | 392 |
| 0.15 | 138 | 184 |
| 0.20 | 81 | 108 |

| | | |
|------|----|----|
| 0.25 | 54 | 72 |
| 0.30 | 39 | 51 |

Thus, if our difference is 20% between those who make the first appointment for an HCV evaluation in the clinic that receives the SAMHSA brochure and the full education groups, we will need 81 patients per group (total 162) to have an 80% power.

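### The protocol and SAP disagree on which video-versus-brochure comparison decides the trial: knowledge retention is the named outcome, first-appointment attendance sets the sample size, and no endpoint is designated primary.

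*SAP*

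**What the plan says.** Five places bear on the question.

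- **Protocol, Hypothesis:** "We anticipate better outcomes in literacy and decision-making capacity with more interactive intervention". Two outcomes are joined, with no ranking.
- **Protocol, Scientific Endpoints:** two numbered aims, health literacy and "Improved decision making among OAT patients". Neither is called primary.
- **Protocol, Study Design:** "The outcome variable is the percentage of the individuals in the two groups that retain HCV-knowledge". The same paragraph says the design evaluates education as a determinant of seeking HCV treatment.
- **Protocol, Procedures Involved:** "We also plan to evaluate the willingness for treatment in people with active hepatitis C infection".
- **SAP, Power/Sample Size:** the table gives patients per group "as a function of the difference in the proportion of patients from both clinics who appear for the first appointment". It adds "The level of significance is 0.05" and concludes that "we will need 81 patients per group (total 162) to have an 80% power" for a 20-point difference.

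The SAP's Statistical analysis text writes one outcome test, between the post-intervention and 1-month questionnaire scores. It names generalized linear mixed-effects models or an alternative, but states no group effect.

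**The concern.** The candidate outcomes can disagree. The video might raise knowledge and leave attendance unchanged, or the reverse. The plan has no rule for what the trial would then conclude. One reader could rest the conclusion on knowledge, because the protocol calls it the outcome variable. Another could rest it on attendance, because only that outcome has a power statement. A third could require both listed endpoints. Nothing in the documents excludes any of these, so the choice could be made once the data are known.

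Two properties of the result are then uncertain. The first is the error rate, if any single success is taken as enough. The second is power, because the sample size was derived for an outcome that the supplied protocol does not list among its endpoints.

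**Working it through.** **1. Candidates set side by side**

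| Outcome | Where named | Between-group test written? | Power given? |
|---|---|---|---|
| Knowledge / literacy | Hypothesis; Scientific Endpoints; outcome variable in Study Design | No; the SAP writes only a comparison of scores over time | No |
| Decision making | Hypothesis; Scientific Endpoints | No; no separate measure described | No |
| Willingness for treatment | Procedures Involved | No | No |
| First appointment | SAP, Power/Sample Size | No | Yes, 80% at 81 per group |

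The outcome named in Study Design and the outcome used for sizing are different, and no row has a written video-minus-brochure test.

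**2. What the 81 per group covers**

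Inputs from the SAP: alpha 0.05, power 0.80, difference 0.20. Sidedness and the lower attendance rate are not stated. I took two-sided and a lower rate of 0.20, because that pair reproduces all ten table cells to within 1. Other lower rates tried from 0.05 to 0.50, one- or two-sided, with or without continuity correction, fit at most eight cells.

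n = [z(0.975)·√(2·p̄·(1−p̄)) + z(0.80)·√(p1(1−p1) + p2(1−p2))]² / d²

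With p1 = 0.20, p2 = 0.40, p̄ = 0.30, d = 0.20:

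n = [1.960·√0.42 + 0.8416·√0.40]² / 0.04 = (1.2702 + 0.5323)² / 0.04 = 81.2

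This matches the stated 81. At the same lower rate a one-sided 0.05 would give 63.9. The sizing therefore spends the full two-sided 0.05 on the attendance comparison.

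**3. Error rate if any one success counts (conditional)**

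Assumptions, none of them in the documents: k tests, each at two-sided 0.05, with equally correlated normal test statistics and no true difference on any outcome. For independent tests the chance of at least one false positive is 1 − 0.95^k. The correlated values come from 1,000,000 simulated draws.

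| False claim that formats differ | corr. 0 | 0.5 | 0.8 |
|---|---|---|---|
| k = 2 (the two listed endpoints) | 0.098 | 0.090 | 0.078 |
| k = 4 (all rows of the first table) | 0.185 | 0.156 | 0.114 |

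Relative to 0.05, the extremes are 0.078/0.05 = 1.6 and 0.185/0.05 = 3.7.

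Counting only errors in favour of video (independent tests: 1 − 0.975^k):

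| False claim that video is better | corr. 0 | 0.5 | 0.8 |
|---|---|---|---|
| k = 2 | 0.049 | 0.045 | 0.039 |
| k = 4 | 0.096 | 0.078 | 0.057 |

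For four candidates that is 1.1 to 1.9 times 0.05. For two it does not exceed 0.05.

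**4. What 81 per group would mean for knowledge**

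If knowledge is a score, compared between independent groups with no dropout, the standardized difference detectable with 80% power is (1.960 + 0.8416)·√(2/81) = 2.8016 × 0.1571 = 0.44 SD. The documents give no SD or expected difference, so this cannot be put in score points.

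If knowledge is the percentage retaining, power for a 20-point difference at 81 per group depends on the lower rate: 0.897 at 0.10, 0.799 at 0.20, 0.743 at 0.30 and 0.725 at 0.40. The 80% carries over only if the retention rate happens to be near the back-calculated attendance rate or lower, or so high that the other group is near its ceiling.

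**The case against.** The best defence is that the protocol is not silent. Study Design names one outcome variable, in the singular, compared between the two groups. That stands: a reader might infer that no passage identifies a deciding comparison, and this would be wrong. The sentence does not settle the matter, however. Its own paragraph gives treatment seeking as the aim, retention is not defined, and the SAP neither analyses nor sizes on the percentage retaining.

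Three stronger readings are tempting, and the documents do not support them.

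- **Four tests are planned at 0.05 each.** The 0.05 is attached to the sample-size table only, and no test is written for decision making or willingness. Decision making has no measure of its own, so willingness or attendance may be how it is meant to be captured. Four is then an upper count.
- **The false-claim rate is about three times alpha.** That needs four tests at a correlation near 0.5, both assumed. It also applies only to a claim that the formats differ. For a false claim that video is better, the same assumptions give 0.078, or 1.6 times 0.05.
- **If both listed endpoints must succeed, the planned power falls to 0.64 to 0.73.** That takes 80% power for each endpoint, whereas the SAP states 80% for attendance alone.

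It is also fair to say that which outcome should lead is the sponsor's decision.

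**Conclusion.** The point holds as a conflict between passages together with a missing designation. Knowledge retention, the literacy and decision-making pair, and first-appointment attendance each have a textual claim to decide the trial. Nothing ranks them or says whether one success is enough.

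The inflation figures are conditional on an any-one-success reading that the documents neither adopt nor exclude. Across two to four tests and correlations 0.8 to 0, the chance of a false claim of difference is 1.6 to 3.7 times 0.05. The directional claim that matches the hypothesis is less affected. The firmer conclusion needs no simulation: the deciding outcome can be chosen after the results, and the stated power belongs to an outcome other than the one Study Design names.

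This should be corrected before analysis. It changes what the trial may conclude, not what data it collects.

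**What to change.** Reconcile the Hypothesis, Scientific Endpoints, Study Design and Procedures Involved sections of the protocol with the SAP by naming one primary between-group contrast, tested at two-sided 0.05.

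1. Study Design points to HCV knowledge at 1 month. Write the video-minus-brochure effect into the SAP's model explicitly, and say whether it is the questionnaire score or the percentage retaining. If the percentage, define retention. Name the arms by content, because Study Design and Procedures Involved attach the letters A and B to opposite interventions.
2. Test first-appointment attendance next, at 0.05, only if the primary is significant.
3. Label decision making, willingness and any second form of the knowledge outcome secondary or exploratory, and report them with confidence intervals.
4. State that the conclusion on video versus brochure rests on the primary contrast.
5. State that 81 per group gives 80% power for attendance only, give the lower attendance rate assumed, and report the detectable difference for knowledge at that size.

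If the sponsor prefers attendance as primary, the 81 can stay and the Study Design sentence should be changed to match.

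**Cost:** mainly wording in both documents plus one sizing check; no new visits or data. A significant result on a non-primary outcome alone could no longer be claimed as confirming the hypothesis. The stated power may not carry over to a knowledge primary, so an unchanged sample size cannot be promised until that check is done.

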| | |
|------------------------------|---|
| Official Title: | Hepatitis C-Video vs. Brochure Education Delivery |
| NCT number: | NCT04204447 |
| Document Type: | Statistical Analysis Plan |
| Date of the Document: | June 30, 2018 |

Statistical Methods

We will initiate the activities on this study with collection of patient demographics at all sites. As part of the preparatory work, we will conduct cognitive testing of the survey instruments to be administered to ensure reliability and accuracy.

The population will be designated into 2 groups i.e. Intervention & Control. The intervention will have the video class intervention and the control will read an HCV educational brochure. We will design both interventions to assess the level of HCV knowledge. Information provided by the brochure and the video will be assessed by the pre/post test questions. These interventions will occur after the pre-test assessment by a designed questionnaire which will include questions on different aspects of hepatitis-C infection disease processes. The last step before analysis will be post interventional assessment with the same questionnaire used for pre-intervention assessment administered 1 month (+/- 2 weeks) after the intervention. All of the intervention and assessment tools will be validated before use. The second assessment may be done over the phone if the subject has no scheduled visits to the clinic during the follow-up period.

At the end we do plan to utilize the data for analysis and manuscript preparation.

Description of the clinics: The two clinics are approximately the same in terms of the percentage of rural patients, of rural HCV seropositive patients, and in the gender distribution. Because patient characteristics differ on the basis of age, race, and ethnicity, we will perform 1:1 matching of the subjects, if possible from the two clinics on these variables.

Statistical analysis: We will conduct exploratory data analysis using box plots for comparison between distributions of continuous variables. Histograms also will provide an additional way of comparing these distributions. Continuous variables are going to be summarized by means and standard deviations or medians and interquartile range, as appropriate. Discrete, that is, categorical variables will be summarized by proportions.

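### The only sample-size justification (81 per group, 80% power) is for making a first HCV-evaluation appointment, an event not defined, collected or analysed elsewhere in the plan; the knowledge outcome has no stated power

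*SAP*

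**What the plan says.** The Power/Sample Size section of the SAP tabulates the number per group "as a function of the difference in the proportion of patients from both clinics who appear for the first appointment", at a significance level of 0.05. Its conclusion begins: "Thus, if our difference is 20% between those who make the first appointment for an HCV evaluation". The two sides of that comparison are then described as patients "in the clinic that receives the SAMHSA brochure and the full education groups". From this the SAP derives its requirement, namely that "we will need 81 patients per group (total 162) to have an 80% power". It gives no assumed attendance rate and does not say whether the test is one- or two-sided.

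Elsewhere the plan concerns knowledge. Study Design in the protocol states: "The outcome variable is the percentage of the individuals in the two groups that retain HCV-knowledge". Scientific Endpoints lists health literacy and decision making. The SAP's Statistical Methods section repeats the knowledge questionnaire, "administered 1 month (+/- 2 weeks) after the intervention", and its analysis text says: "We will test the differences between the scores obtained on the post-intervention assessment and the 1-month follow up assessment". The only binary outcome modelled explicitly in the SAP is HCV seropositivity.

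**The concern.** A power statement should belong to a comparison that the plan will make on data it will collect. Here the stated 80% belongs to an event that appears only in the power section. Knowledge, which the study does measure, has no target difference, assumed rate, standard deviation or power.

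A reader therefore cannot tell what difference in retention or score 162 patients could detect. A null result on knowledge could not be set against any planned detectable difference, and the 80% could be misread as applying to knowledge.

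**Working it through.** **1. Reproducing the plan's figure.** Inputs from the SAP: significance level 0.05, differences of 0.10 to 0.30, power 0.80 and 0.90. Equal groups follow from the 1:1 design. The lower rate p1 is not given, so it was searched for. With p̄ = (p1+p2)/2 and d = p2−p1, the pooled-variance formula is

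n = [1.960·√(2p̄(1−p̄)) + z_power·√(p1(1−p1)+p2(1−p2))]² / d².

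For 20% vs 40% at 80% power: n = (1.960·√0.42 + 0.842·√0.40)² / 0.04 = 81.22. All ten cells, with p1 = 0.20 and a two-sided test:

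| Difference | Computed (80% / 90%) | SAP (80% / 90%) |
|---|---|---|
| 0.10 | 293.15 / 391.95 | 293 / 392 |
| 0.15 | 137.91 / 184.13 | 138 / 184 |
| 0.20 | 81.22 / 108.24 | 81 / 108 |
| 0.25 | 53.90 / 71.66 | 54 / 72 |
| 0.30 | 38.48 / 51.01 | 39 / 51 |

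Every cell agrees to within one patient, and this is the best fit found. It is still an inference: a one-sided, continuity-corrected calculation with a lower rate near 28% fits almost as well.

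**2. Tracing the event through the documents.**

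- *Aim.* Background and Study Design in the protocol speak of pursuing HCV evaluation and seeking treatment. Attendance is related to this, but neither section defines it as a measure.
- *Collection.* The chart review covers demographics, mental health, substance use, HCV status and employment. Appointments are not listed. Procedures Involved places this review before patients are designated to groups, so as scheduled it cannot capture an appointment made after the education.
- *Nearest measure.* Procedures Involved adds a questionnaire section on willingness for treatment for patients with a history of HCV. Willingness is not attendance.
- *Analysis.* The SAP covers questionnaire scores and seropositivity. It gives no time window, denominator or model for attendance.

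**3. What 81 per group gives for retention.** Two-sided 0.05, independent evaluable patients, 20-point difference:

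power = Φ{[d√n − 1.960·√(2p̄(1−p̄))] / √(p1(1−p1)+p2(1−p2))}.

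At 40% vs 60%: (0.2·9 − 1.960·√0.5)/√0.48 = (1.800 − 1.386)/0.693 = 0.598, so power is 72.5%.

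| Rates | n = 81 | n = 73 | n = 65 |
|---|---|---|---|
| 10% vs 30% | 89.7% | 86.3% | 82.1% |
| 20% vs 40% | 79.9% | 75.6% | 70.6% |
| 30% vs 50% | 74.3% | 69.8% | 64.6% |
| 40% vs 60% | 72.5% | 67.9% | 62.8% |

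The values are symmetric above this: 50% vs 70% equals 30% vs 50%, and so on up to 70% vs 90%. Below 10%, power rises further (95.3% at 5% vs 25%). At 40% vs 60%, 80% power needs 96.9, i.e. 97 per group. The columns for 73 and 65 apply an assumed 10% or 20% loss (81 × 0.9 = 72.9; 81 × 0.8 = 64.8); the documents give no loss rate.

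**4. What 81 per group gives for a 1-month score.** The standardised difference detectable between groups with 80% power is (1.960+0.842)·√(2/n): 0.44 at 81, 0.46 at 73 and 0.49 at 65. If the pre-test is used as a covariate and its correlation with the 1-month score is assumed to be 0.5, the figure at 81 is 0.44·√(1−0.25) = 0.38.

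**The case against.** The best defence is that attendance is a reasonable expression of the treatment-seeking aim, and that the power paragraph itself posits a comparison of attendance between brochure and full education. Both points stand, so it would go too far to call the event foreign to the study or to say that no comparison is mentioned anywhere. But an aim and a sentence in a power section do not supply data collection, a time window or an analysis.

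A second defence is that retention is also a percentage, so the table could serve for it. Numerically it could: if the lower retention rate were 20% or 60%, 81 per group would give about 80% power. The SAP does not make that transfer or state a rate for retention, and the test it specifies is on scores.

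Three stronger readings are tempting and not supported:

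- *That 81 is miscalculated.* Rounding up 81.22 gives 82, but 81 gives 79.9% power, which is immaterial.
- *That 162 patients are too few for knowledge.* The documents give no target difference against which to judge this.
- *That arms follow clinics, so a cluster adjustment was omitted.* The power paragraph's wording points that way, but the SAP also says "we will perform 1:1 matching of the subjects, if possible from the two clinics on these variables", and the assignment of arms to clinics is never settled.

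**Conclusion.** The point holds as a mismatch between the stated power and the outcome the protocol names. It should be corrected, but it does not invalidate the study and biases no estimate.

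Its size depends on which knowledge outcome is chosen. For a 20-point difference in retention, the true power may lie on either side of the advertised 80%, with a minimum of 72.5%. For a score, it is a matter of stating that about 0.44 standard deviations is detectable.

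These figures assume a two-sided 0.05 test and 81 evaluable, independent patients per group. The retention rates, loss rates and pre/post correlation are assumptions of this review. No between-clinic variation or effect of matching is included. The conclusion is limited to the supplied text.

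**What to change.** Name one primary outcome in the SAP, and give it both a video-versus-brochure analysis and a matching power statement. Restating power alone would repeat the defect, because the SAP's only explicit score test compares time points and it describes no analysis of retention.

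1. *If the outcome is the percentage retaining knowledge:* define retention, add the between-group comparison of that proportion at 1 month, state the assumed brochure-group rate, and replace the 80% claim with the power at that rate.
2. *If the outcome is the 1-month score:* add an explicit group effect to the model, for example adjusted for the pre-test score, which is already collected. State 80% power for a standardised difference of 0.44 unadjusted, or about 0.38 under an assumed correlation of 0.5.

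In either case, say whether 81 means enrolled or evaluable, state the assumed loss before the 1-month assessment, and note that between-clinic variation and matching are not reflected.

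Then remove the first-appointment claim. Alternatively, relabel it as secondary, but only if attendance is defined (event, window and denominator, since the inclusion criteria do not require HCV infection), extracted after the intervention, and compared between groups with a stated rate.

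The cost is SAP wording and a possibly less favourable stated power. Keeping attendance also needs a new chart extraction after the intervention. If the team wants 81 evaluable per group, enrolment becomes 81/0.9 = 90 or 81/0.8 = 101.25, i.e. 102, per group at an assumed 10% or 20% loss.

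### The plan does not say what is assigned to video or brochure, or how; if each clinic gives one format, the stated 5% level and 80% power require no variation between clinics

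*SAP*

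**What the plan says.** On assignment, the protocol (Procedures Involved) says "After that information is collected, we plan to designate the population in 2 groups i.e. Intervention & Control". The SAP (Statistical Methods) says "The population will be designated into 2 groups i.e. Intervention & Control". Neither gives a unit, an allocation rule or any mention of randomisation. The protocol (Study Design) calls the study observational, with two groups matched 1:1, and expects two or three clinics.

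On the clinics, the SAP describes two: "The two clinics are approximately the same in terms of the percentage of rural patients". It reports similarity also for rural HCV seropositivity and gender. For age, race and ethnicity, where patients differ, "we will perform 1:1 matching of the subjects, if possible from the two clinics on these variables".

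On sample size, the SAP tabulates patients per group against "the difference in the proportion of patients from both clinics who appear for the first appointment". It then takes a 20-point difference "in the clinic that receives the SAMHSA brochure and the full education groups" and arrives at 81 per group, 162 in total, for 80% power at a significance level of 0.05.

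On the score model, the SAP says "We will include demographic factors and other covariates as appropriate". Clinic is not named there.

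**The concern.** If each clinic gives one format, every difference between the clinics, such as referral practice or access to appointments, is part of the video-brochure contrast. A clinic difference could be reported as a format effect, or could hide one. Matching on age, race and ethnicity does not remove differences of this kind. The sample-size outcome, attendance at a first appointment, is directly open to them.

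If both formats are given within each clinic, clinic can be taken into account, but the plan would have to say so. As written, the reader cannot tell which case applies, and so cannot tell whether the stated level and power belong to this design.

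**Working it through.** **1. What the text supports**

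| Points to one format per clinic | Leaves patient-level assignment open |
|---|---|
| SAP, Power/Sample Size: a clinic is said to receive the brochure | Protocol, Procedures Involved: "The study flyers for advertisement will be distributed at all the clinic sites"; consent and chart review follow, and groups are formed only after that |
| SAP, Description of the clinics: subjects matched across the two clinics | SAP, Statistical Methods: the population is designated, with no unit given |
| Protocol, Study Design: matching factors chosen between clinics | SAP, Power/Sample Size: the phrase about both clinics could mean patients pooled over clinics |

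Matching across clinics works as group matching most naturally if the clinics are the groups. That makes the left column the more likely reading, but not a certain one.

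**2. The plan's 81 per group**

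The documents give alpha 0.05, power 0.80 and a difference of 0.20. They do not give the base rate or the sidedness. Assume 20% vs 40%, two-sided, pooled two-proportion formula:

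n = [1.96·√(2p̄(1−p̄)) + 0.8416·√(p₁(1−p₁) + p₂(1−p₂))]² / (p₂−p₁)²

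With p̄ = 0.30: (1.96·√0.42 + 0.8416·√0.40)² / 0.04 = (1.2702 + 0.5323)² / 0.04 = 81.2.

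| Difference | Computed, 80% / 90% | SAP |
|---|---|---|
| 0.10 | 293.2 / 391.9 | 293 / 392 |
| 0.15 | 137.9 / 184.1 | 138 / 184 |
| 0.20 | 81.2 / 108.2 | 81 / 108 |
| 0.25 | 53.9 / 71.7 | 54 / 72 |
| 0.30 | 38.5 / 51.0 | 39 / 51 |

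All ten cells agree within one patient; power at 81 is 79.9%. The formula is unchanged when each p is replaced by 1−p, so a fixed upper rate of 80% (60% vs 80% for this row) gives the same ten values. A one-sided formula with continuity correction at a base rate of about 27% also comes close. The base rate is therefore an inference. Every version that fits treats patients as independent, with no clinic term.

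**3. Estimability with one format per clinic**

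With two clinics, the columns for intercept, format and clinic have rank 2 of 3, so clinic cannot be estimated beside format. There are 0 degrees of freedom between clinics within format. With three clinics, one format still rests on a single clinic and 1 degree of freedom remains.

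**4. Type I error with one clinic of 81 per format**

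The documents give no intraclass correlation (ICC), so a range is assumed. The design effect is DE = 1 + (81−1)·ICC. The type I error of the unadjusted test is 2[1 − Φ(1.96/√DE)]. For ICC 0.01: DE = 1.8, 1.96/1.342 = 1.461, result 0.144.

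| ICC | Between-clinic SD at 20%, √(ICC·0.2·0.8), points | DE | Type I error, formula | Simulated, 20% rate |
|---|---|---|---|---|
| 0 | 0 | 1 | 0.050 | 0.051 |
| 0.001 | 1.3 | 1.08 | 0.059 | 0.059 |
| 0.005 | 2.8 | 1.4 | 0.098 | 0.098 |
| 0.01 | 4.0 | 1.8 | 0.144 | 0.145 |
| 0.02 | 5.7 | 2.6 | 0.224 | 0.226 |
| 0.05 | 8.9 | 5.0 | 0.381 | 0.388 |

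(Beta-binomial simulation, 1,000,000 runs.)

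**5. The same point without an ICC**

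Suppose format has no effect and the clinics differ from an assumed 20%. For a 10-point gap, p̄ = 0.25. The null standard error is √(0.375/81) = 0.0680 and the actual one is √(0.37/81) = 0.0676. P(significant) = Φ[(0.10 − 1.96·0.0680)/0.0676] ≈ 0.31. For gaps of 5, 10 and 15 points it is about 12, 31 and 57%.

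In the other direction, a true 20-point gain offset by a 10-point clinic deficit is seen as 20% vs 30%, and is detected about 31% of the time.

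**6. Both formats within each clinic**

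Simulation with 162 patients, 81 per clinic, 20% vs 40%, and a Mantel-Haenszel test stratified by clinic. Unequal splits run in opposite directions in the two clinics, so the groups stay about equal overall.

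| Split within clinic | Power |
|---|---|
| 50/50 | 0.80 |
| 70/30 | 0.73 |
| 75/25 | 0.68 |
| 80/20 | 0.61 |

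Type I error at an even split is about 0.05. These figures assume that assignment is unrelated to prognosis.

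**The case against.** **The clinic-level reading rests on loose text.** The SAP sentence sets one clinic against plural groups and uses names for the two formats found nowhere else. Attendance at a first appointment is not a named endpoint of the protocol. This stands, and it is why the confounding is stated conditionally. A reader might infer that the study certainly assigns by clinic; the order of steps in Procedures Involved does not allow that.

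**The design is declared observational, and the clinics are compared and matched.** This is true, but an observational comparison must still say how exposure arises. Matching on three patient characteristics, where possible, does not decide who receives which format.

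**Clinic could enter the model as a covariate.** It is unnamed rather than excluded, so it would be wrong to say that the SAP leaves it out. With one format per clinic, however, adding it would achieve nothing.

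**The pre-test helps.** This stands. A reader might infer that no analysis could separate clinic from format for any outcome. For knowledge that goes too far: the same questionnaire is given before and after, so a stable clinic difference in level can be seen and removed. A clinic difference in change cannot.

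**Giving both formats in each clinic is not a complete cure.** This also stands. A reader might infer that 81 per group would then be sound without further conditions. No randomisation is mentioned, and a clinic term does not remove selection of patients into formats.

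**Conclusion.** The concern holds in two parts. Without condition: the unit and method of assignment are missing, and the passages that bear on them point in different directions. On condition of one format per clinic, which is the more likely reading: with two clinics the format effect on attendance cannot be separated from clinic, and the stated level and power are not properties of the design unless between-clinic variation is zero.

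The size depends on figures that the documents do not give. The type I errors of 6 to 38% rest on ICCs assumed between 0.001 and 0.05 and on one clinic of 81 per format; three clinics would change the values without removing the problem. The fixed-gap results of 12, 31 and 57% rest on an assumed 20% rate. They apply to first-appointment attendance, not to knowledge scores adjusted for the pre-test. The arithmetic of the sample-size table is not in dispute for independent patients.

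**What to change.** State the unit and method of assignment, and reconcile Study Design and Procedures Involved in the protocol with the SAP's description of the clinics and its sample-size paragraph. This includes the group labels: group A has the video in Study Design, but group B has it in Procedures Involved. State the base rate and sidedness behind the table.

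1. **If both formats are given within each clinic:** include clinic as a fixed effect in the format comparison and the pre-test score as a covariate in the knowledge analysis. Say how the 1:1 matching across clinics will be used. Keep the 81 per group only on the stated conditions: the assumed rates, rough balance of formats within clinic, and assignment that does not depend on prognosis. If patients are not randomised, say that selection into format remains a limit.

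2. **If one format per clinic is kept:** withdraw the 80% power statement and adjust the knowledge analysis for the pre-test score. State that a format difference cannot be separated from a clinic effect (for knowledge, from a clinic difference in change).

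Both options cost wording and analysis changes only; option 2 gives up the power claim. Moving from one format per clinic to both in each would need the video and a facilitator at every site, so it is not asked for.
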